Objectives:	The objective of this observational prospective study is to systematically document the clinical outcomes of Zimmer MotionLoc Screws for Periarticular Locking Plate System applied to distal tibia fracture treatment and confirm safety and performance of the screws.
Endpoints:	
Primary endpoint: Radiologic & clinical fracture healing at three months post-surgery.
 
Secondary endpoints:
 
 • Complications • Radiologic & clinical fracture healing at 6 weeks, 3, 6, and 12 months post-surgery. • Callus size & distribution at 6 weeks, 3, 6, and 12 months post-surgery.
Target Population:	Patients with distal tibia fractures (AO 43-A and C) requiring surgical intervention eligible for locked plating.
Study Design:	Prospective, global, multi-center, non-randomized, non-controlled
Number of Cases:	Patient enrollment is limited to one year or 40 subjects whichever is reached first. Per site enrollment will be limited to 15 subjects.
Length of Study:	2 years (1 year enrollment plus 1 year follow-up): Required follow-up visits at 6 weeks, 3, 6, and 12 months post-surgery.
Study Device:	Zimmer® Periarticular Distal Tibial Locking Plates (medial and/or lateral) in conjunction with Zimmer® MotionLoc® Screw for the Periarticular Locking Plate System.
Scores:	FIX-IT
Documentation:	Electronic Case Report Forms
Statistical Reporting:	Data collected will be summarized and reported to each participating investigator. Statistical analysis will be conducted by Zimmer Biomet or its designee.

II. Introduction

The optimal treatment for distal tibia fractures remains controversial. A recent systematic literature review found a reduced risk for malalignment for plate fixation compared to intramedullary nailing [2]. However, for bone union, wound complications and superficial infection or deep infection no statistically significant differences were identified.

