In the last decade locking plates gained popularity not only for distal tibia fractures but fracture treatment in general. Recent studies raised concerns because of the inherent stiffness of these locking devices and found they might suppress fracture healing [3][4][5]. To address this issue the concept of Far Cortical Locking (FCL) was developed [6][7] and has been commercially available since 2010 in the *Zimmer MotionLoc* Screw for NCB[®] Polyaxial Locking Plate System and since 2014 in the *Zimmer MotionLoc* Screw for *Zimmer* Periarticular Locking Plate System (Zimmer Inc.).

FCL screws lock rigidly into the plate and into the far cortex, but retain a controlled motion envelope in the near cortex. The screws have an elastic shaft portion that can deflect within this motion envelope. This flexion of FCL screw shafts induces symmetric axial motion at the fracture site in response to load bearing. FCL screws are optimized to reduce the initial stiffness of a locked plating construct while retaining its construct and fixation strength. *MotionLoc* Screws for *Zimmer* Periarticular Locking Plate System reduce the locked plating construct stiffness by more than 58% while retaining construct strength [8].

Recently, a prospective observational clinical study in 31 distal femur fractures treated with *Zimmer MotionLoc* Screws for NCB Polyaxial Locking Plate System has shown a fracture healing rate of 97% (30 out of 31) after a 6 month follow up period with no implant and fixation failure.

The purpose of this observational prospective study is to systematically document the clinical outcomes of *Zimmer MotionLoc* Screws for Periarticular Locking Plate System applied in distal tibia fracture treatment and confirm safety and performance of the screws.

III. Study Objectives

The objective of this observational prospective study is to systematically document the clinical outcome of *Zimmer MotionLoc* Screws for Periarticular Locking Plate System applied in distal tibia fracture treatment and confirm safety and performance.

Primary Endpoint:

- Radiographic & clinical fracture healing at 3 months post-surgery.

Secondary Endpoints:

- Complications
- Radiologic & clinical fracture healing at 6 weeks, 3, 6, and 12 months post-surgery.
- Callus size & distribution at 6 weeks, 3, 6, and 12 months post-surgery.

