Radiologic fracture healing is defined as bridging of three of the four cortices as seen on x-ray/CT [10][11]. Clinical healing will be assessed using the Function Index for Trauma (FIX-IT) [12]. The

FIX-IT instrument quantifies clinical healing by assessing weight-bearing and fracture site pain on an ordinal scale. It has been initially validated in patients with tibia and femur fractures [12].

Callus size of the anterior, posterior, and medial aspect will be assessed for each time point using a validated and published computational method [13].

IV. Study Device

Description of the Device

Zimmer MotionLoc is a screw technology developed to reduce construct stiffness of locking plates while retaining construct strength. Further, it creates constructs that allow nearly parallel interfragmentary motion compared to standard locking screws constructs which allow motion under load at the far cortex while motion at the near cortex remains negligible. The parallel interfragmentary motion creates an environment that is thought to promote a symmetric callus [9]. The *Zimmer MotionLoc* screw is designed for use with *Zimmer's* Periarticular Locking Plate System. In this trial the 3.5mm diameter stainless steel version will be used. The screw is available from 22 to 44mm and 22 to 60mm length in two millimeter increments, non-sterile and sterile, respectively. The *Zimmer MotionLoc* Screw for the Periarticular Locking Plate System (Figure 1) has a standard cortical thread section (self-tapping, single helix); an expansion section, intended to create the gap for motion in the near cortex; a mid-section thread with a reduced core-diameter and reverse cutting flutes to aid in screw removal; a non-threaded collar section; and a double lead threaded head for engagement in the plate.

[figure not shown]

Figure 1: *Zimmer MotionLoc* Screw for the *Zimmer* Periarticular Locking Plate System

Further product information is available in the surgical technique or instruction for use (see investigator binder).

V. Study Design

General Study Design

This study is designed to be prospective. It is a multi-center, global, non-randomized, and non-controlled study. Institutional Review Board/Ethics Committee (IRB/EC) approval for each clinical site must be obtained prior to conducting this research. The primary outcome will be clinical & radiological fracture healing at three months post-surgery.

Study Duration

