Patient eligibility for enrollment will be determined for consenting candidates based on the inclusion/exclusion criteria. Patients must meet all of the inclusion criteria and none of the exclusion criteria in order to be offered enrollment into the study. Determination of eligibility may include an interview to assess significant patient surgical/medical history, history of present illness/injury, evaluation of present pain and functional capacity, and a radiographic assessment. All eligible patients will be offered enrollment into the study. For the purposes of this clinical study, patients will be considered subjects after enrollment has been completed.

Subject Enrollment Log

A Subject Enrollment Log must be maintained throughout the study and is included in the Investigator Binder. All patients enrolled in the study must be entered into the Enrollment Log and the "Inclusion/Exclusion" form must be completed. Patients must be entered into the Enrollment Log sequentially.

Baseline/Preoperative Assessment

Following enrollment, demographic and injury classification data will be entered into the “Demographic Information & Injury Classification” set of forms.

Surgical Technique

Implantation will be performed in accordance to the manufacturer’s surgical technique. The distal articular segment will be fixed to the plate(s) (medial and/or lateral *Zimmer* Periarticular Distal Tibial Locking Plate) with the appropriate number of standard locking screws. All fractures will be treated with a “bridge plating” strategy - working length (empty screw holes between the distal and proximal segment, see Figure) is up to investigator/surgeon discretion. A minimum of three MotionLoc screws will be applied into the proximal shaft segment. No inter-fragmentary lag screws are permitted across non-articular fractures.

[figure not shown]

Figure 2: Working length

After surgery, intraoperative data will be entered into the “Operative Information” set of forms.

Postoperative Care

Weight bearing will be at the surgeon’s discretion based on the degree of fracture healing.

Surgery until Discharge

After surgery, but before the subject leaves the hospital, standard anteroposterior and lateral x-rays of the operated side must be obtained and the “Discharge” set of forms must be completed.

Follow-up Procedures (Data Collection)

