Follow-up evaluations will be performed at 6 weeks (± 14 days), 3 months (± 14 days), 6 months (± 30 days) and 12 months (± 30 days) post-surgery. Standard anteroposterior and lateral x-rays of the operated side must be obtained at each follow-up. If the treating surgeon is unable to adequately assess cortical healing due to radiographic obstruction of the implant(s), additional x-ray(s) should be performed. At 3 months a CT scan of the fracture site must be performed in addition. The “Follow-up” set of forms must be completed at each follow-up time point. This includes the assessment of radiologic fracture healing. At 6 weeks, 3, 6 and 12 months, the surgeon must assess the FIX-IT Score and document on the corresponding set of forms. At the 12

month follow-up the “Study Completion” form must be completed additionally. Copies of the original x-ray films and CT scans must be sent to the Sponsor.

Patient Withdrawal

Patient withdrawal has to be documented on the “Study Completion” form. In particular the reason for withdrawal must be documented. The occurrence of any of the following situations gives reason to withdraw a patient from the study:

- Voluntary patient withdrawal. Patients are at liberty to withdraw from the study at any time and for any reason without affecting future treatment.
- Development of a concurrent condition which would interfere with the patient's continued participation.
- Reoperation including complete removal of study device(s).
- Patient is non-compliant.

Lost to Follow-up

Patients will be considered lost to follow-up after they have missed a visit and a reasonable number of attempts to locate and evaluate them have failed. This has to be documented on the “Study Completion” form and in particular the reason should be documented. Patients lost to follow-up will not be replaced within the study.

Minimization of Subjects Lost to Follow-Up

Subject follow-up is extremely important for the conduct of a clinical study. The expectation is to maintain the highest rate of follow-up compliance possible throughout this study. No replacement is foreseen for any patient lost to follow-up. In an effort to minimize lost-to-follow-up subjects, the following recommendations and/or study requirements are essential to ensure proper patient selection and compliance:

1. Patient Eligibility: Subjects will be selected according to the inclusion/exclusion criteria detailed in Section 8 and are expected to return for all follow-up visits.

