2. Patients Counseled: Patients will be counseled during the Informed Consent process on the importance of returning for follow-up visits.
3. Patient Exclusion: Patients who are not willing to return for study required follow-up visits and/or are not willing to comply with the follow-up schedule will not be considered for enrollment into the study.
4. Subject Due Listings: In addition to proper patient selection, Zimmer Biomet will provide subject due notices to the sites on a regular basis in order to track each study participant and monitor adherence to the required follow-up visit timeframes. The subject due listings will facilitate scheduling the subjects for their return office visits.
5. Contact Tracking: Attempts to contact subjects will be documented in the study subject's medical record. It is recommended that the first three attempts be made by telephone. If

after three calls, contact has not been successful, the below is required prior to terminating the study subject from the study:

Recommended Contact Attempts

If	Then
a response is not received from 3 phone calls	the investigator should send a letter to the subject explaining the follow-up agreement per informed consent.
a response is not received from the investigator’s first letter	the investigator should send a certified letter to the subject.
a response is not received from the investigator’s certified letter	the investigator should use any additional contacts provided by the subject to contact the subject.
all attempts to contact the subject are unsuccessful or the subject is contacted and chooses to withdraw from the study	the “Study Completion” form will be completed and will specify the reason the subject is no longer participating in this study.

Radiographic Management

All radiographic imaging performed according to the protocol will be reviewed and evaluated by the investigator or qualified designee at the time of the post-operative assessment for standard patient management purposes. If a radiographic adverse event is identified by the Investigator during the course of the investigation, the Investigator must document the event and report the radiographic findings on a Complication Case Report Form for Sponsor review. It is possible that radiographs taken within this study could be used for future regulatory submissions and/or product evaluations, and may therefore require radiographic review by an unbiased independent review.

Recommended Revision Procedure

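### Does the primary endpoint need a stated rule for combining radiologic and clinical healing, with a FIX-IT value that counts as healed?

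*Combined protocol and SAP*

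**What the plan says.** The synopsis, Section III and Section V (General Study Design) all give the primary endpoint as radiologic and clinical healing, joined by an ampersand. Section V reads: "The primary outcome will be clinical & radiological fracture healing at three months post-surgery".

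Section III defines the two halves differently.

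- Radiologic: "Radiologic fracture healing is defined as bridging of three of the four cortices as seen on x-ray/CT". This is a yes/no rule.
- Clinical: the "FIX-IT instrument quantifies clinical healing by assessing weight-bearing and fracture site pain on an ordinal scale". Neither a score range nor a healed value is given.

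The synopsis lists FIX-IT under Scores. Section VII promises descriptive presentation: frequencies and percentages for categorical data, the usual summaries for continuous data, and Wilcoxon or Mann-Whitney tests for non-parametric comparisons. Its example is a score compared between visits. It names no primary hypothesis, target healing rate or success criterion.

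On who does what, Section VI leaves weight bearing to the surgeon's "discretion based on the degree of fracture healing". At each follow-up visit "the surgeon must assess the FIX-IT Score and document on the corresponding set of forms". Images are read by the investigator or a designee "at the time of the post-operative assessment for standard patient management purposes". The synopsis adds: "Statistical analysis will be conducted by Zimmer Biomet or its designee". Appendix A (Case Report Forms) is present as a heading only.

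**The concern.** A primary endpoint written as two things joined by an ampersand invites the question of what is counted. If one healing rate per subject is meant, an ordinal score has to be cut somewhere and a rule has to say whether both halves must be met. The text supplies neither. With no control group and analysis in the sponsor's hands, both could in principle be chosen after the data are seen. The Introduction adds to the doubt by reporting an earlier femur study as a single healing rate (97%, 30 of 31), so a reader may expect the same form here. The same pair of measures is also a secondary endpoint at 6 weeks, 3, 6 and 12 months.

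The second worry is circularity. Weight bearing is one of the two things FIX-IT assesses. The surgeon permits weight bearing according to how far healing has progressed, and the surgeon also scores FIX-IT. The clinical half could then partly restate the surgeon's view of healing, and differences in practice across about 8 sites could enter it.

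**Working it through.** **1. The plan's own figure.** Section VII expects 5 patients per site in one year at 8 sites: 8 × 5 = 40, which reproduces. It is an accrual estimate. No effect size, power or precision is stated, so 40 does not depend on how the endpoint is defined.

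**2. What each reading needs.**

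| Reading | Support in the text | Needs a FIX-IT cut-off? |
|---|---|---|
| Side by side | FIX-IT listed as a score; ordinal description; descriptive methods; score comparison as the Wilcoxon example | No |
| Per-subject composite | The ampersand; the singular word outcome in Section V; the femur study's single rate | Yes, plus a combining rule |

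The femur rate is weak support, because the Introduction does not say how healing was defined there or that two components were combined. The side-by-side reading can be carried out from the text as it stands.

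**3. How much a cut-off could move a composite (illustration; every rate is assumed).** Let r be the radiologic rate and c the share passing the FIX-IT cut-off, with c from 50% to 90%. If both must be met, the composite is min(r, c) when the halves are nested and r × c when they are independent. Half-widths are those of exact (Clopper-Pearson) 95% intervals at rate r, for the planned maximum of 40 and the enrolment floor of 30.

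| r | Nested: range (swing) | Independent: range (swing) | Half-width, n=40 | Half-width, n=30 |
|---|---|---|---|---|
| 40% | 40–40% (0) | 20–36% (16) | 15.9 | 18.4 |
| 50% | 50–50% (0) | 25–45% (20) | 16.2 | 18.7 |
| 60% | 50–60% (10) | 30–54% (24) | 15.9 | 18.4 |
| 70% | 50–70% (20) | 35–63% (28) | 15.0 | 17.3 |
| 80% | 50–80% (30) | 40–72% (32) | 13.3 | 15.4 |

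Example at r = 60%: nested, min(0.6, 0.5) = 0.50 to min(0.6, 0.9) = 0.60; independent, 0.6 × 0.5 = 0.30 to 0.6 × 0.9 = 0.54. The interval for 24/40 is 43.3–75.1%.

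From r = 40% to 60%, the nested swings (0, 0 and 10 points) lie inside the half-width. Only independence gives larger ones, and even then the 16 points at r = 40% only match the half-width at n = 40. Independence is implausible for two measures of the same fracture. Nested swings above the half-width (20 and 30 points) need assumed radiologic rates of 70% to 80%.

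**4. Widest possible gap between the readings.** With each half at an assumed 60%, side-by-side reporting shows 60% and 60%. A both-met rate lies between max(0, 0.6 + 0.6 − 1) = 20% (8/40) and min(0.6, 0.6) = 60% (24/40), and is 0.6 × 0.6 = 36% under independence. The lower end needs the halves to disagree as often as arithmetic allows.

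The counts out of 40 assume complete follow-up and one fracture per subject, although Section VI admits bilateral fractures and does not replace losses.

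**5. Weight-bearing link.** The text does not say whether FIX-IT records permitted or achieved weight bearing, or whether one person does both assessments. That depends on the instrument's source and the forms, neither of which is available. Neither direction nor size can be derived.

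**The case for a change.** The best case for a change is that a descriptive percentage still needs a numerator. Section V speaks of one primary outcome, the stated aim is to confirm safety and performance, and two analysts could follow this plan and report different headline results. Section IX also lets the sponsor stop the study if interim results depart from expected outcomes or statistical endpoints, which seems to presuppose a defined endpoint. Stating the choice would take a few sentences.

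The factual part stands: no available section gives a combining rule or a healed value for FIX-IT, though Appendix A may. The consequence is weaker. An analyst who follows the methods section reports the cortical-bridging percentage and summarises the score, and nothing in that result is wrong. The stopping clause sets no threshold on a composite rate, so no decision turns on one. Stating the choice would record a preference without correcting a result the plan would otherwise get wrong.

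On circularity, the inference from Section VI is fair, but agreement between the halves is expected anyway. Scoring FIX-IT before the images are read would not remove the influence of instructions given at earlier visits, and images are also read for patient care. Extra form fields or separate reporting of the FIX-IT domains would repair no planned result. The mandatory 3-month CT and the image copies sent to the sponsor allow the radiologic half to be re-read, but that would not help FIX-IT.

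One looseness remains under either reading: cortical bridging may be judged on x-ray or CT, both are taken at 3 months, and the text does not say which governs. A combining rule would not settle that.

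**Conclusion.** No change to the plan follows. The missing combining rule and healed value are a gap in detail that analysts can fill sensibly from the plan's own methods: a radiologic percentage beside a descriptive FIX-IT summary. No stated hypothesis, target rate, power or type I error is affected.

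The size of the gap cannot be derived from the documents. The 0 to 32 point range rests wholly on assumed radiologic rates (40% to 80%), assumed pass shares (50% to 90%) and an assumed dependence between the halves. The conclusion assumes that side-by-side reporting is what the study delivers. A single combined rate with a cut-off chosen after the data were seen would deserve the caution set out above. The weight-bearing link is a point to bear in mind when reading the FIX-IT results, with no direction or size that the documents support.

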If a device has to be removed¹, the investigator will choose the best revision treatment method for the subject. Before revision surgery, the Investigator must document any significant radiographic findings related to the need for revision. Additionally, once the revision surgery has been completed, the Investigator must complete an Adverse Event CRF, as well as a Study Completion CRF, terminating the subject from the study.

¹Device removal after fracture healing, upon patient request or as part of standard treatment, is not considered a “Recommended Revision Procedure”.

Explanted Device Return

All components removed, except the devices removed after fracture healing upon patient request or as part of standard treatment, should be returned to Zimmer Biomet for analysis. The Investigator must notify the Clinical Study Manager prior to the return of any device. Properly prepared specimens are to be sent to:

Zimmer Biomet
Attention: Product Services Department
[name]
[name]

VII. Statistical Methods

General Statistical Methods

Considering the inclusion and exclusion criteria, per study site an enrollment of 5 patients in one year can be expected. Within one year of enrollment at 8 study sites this equals to 40 patients in total. For the purpose of this observational study this number of patients is considered to be sufficient to document first clinical outcome and assess safety and performance. Collected data will be presented descriptively. For categorical data, frequency and percentage will be calculated. For continuous data, mean, standard deviation, median, minimum and maximum will be calculated.

Comparative assessment

For comparative assessments of any non-parametric data (e.g. score between different follow-up time points) the Wilcoxon test will be used for paired, and the Mann-Whitney test for unpaired data. A significance level of $p=0.05$ will be set.

VIII. Risk Analysis

Zimmer MotionLoc Screws for the *Zimmer* Periarticular Locking Plate System have been commercially available since April 2014. The devices involved are used in accordance with the cleared indications. There are no anticipated risks specific to study participation other than the potential loss of confidentiality. There are no experimental procedures in this study and participation is not anticipated to affect the medical treatment of enrolled subjects.

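### The protocol does not say whether a subject whose plate is removed after healing stays in follow-up, so 12-month data could be lost selectively among healed subjects

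*Combined protocol and SAP*

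**What the plan says.** Four places in the protocol bear on this.

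- **Section VI, Patient Withdrawal.** The list is introduced by "The occurrence of any of the following situations gives reason to withdraw a patient from the study" and one of its items is "Reoperation including complete removal of study device(s)". The item does not distinguish removal for failure from removal after healing.
- **Section VI, Recommended Revision Procedure.** After revision surgery the investigator completes an adverse event form "as well as a Study Completion CRF, terminating the subject from the study". Footnote 1 states that removal once the fracture has healed, at the patient's wish or as routine care, does not count as such a procedure.
- **Section VI, Explanted Device Return.** The same exception appears again: "All components removed, except the devices removed after fracture healing upon patient request or as part of standard treatment, should be returned".
- **Section III, Study Objectives.** The primary endpoint is "Radiographic & clinical fracture healing at 3 months post-surgery". The secondary endpoints include complications, callus, and "Radiologic & clinical fracture healing at 6 weeks, 3, 6, and 12 months post-surgery".

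Section VI, Follow-up Procedures sets the late visits at "6 months (± 30 days) and 12 months (± 30 days) post-surgery". Section VII plans descriptive summaries and paired Wilcoxon tests of scores between time points. It gives no rule for subjects who were withdrawn or whose data are missing.

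**The concern.** The protocol foresees routine removal after healing and exempts it twice: from the revision procedure and from device return. It does not exempt it in the withdrawal list, where the exemption would decide whether data collection continues. A subject healed at 6 months whose plate is taken out at 9 months could be withdrawn by one site and followed to month 12 by another, with neither clearly in breach.

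The loss would not be random, since removal after healing can occur only in subjects who have healed. Three things are at stake: 12-month healing and callus status in those subjects, their pairs in any comparison of scores with month 12, and complications after the removal operation. The study is global and multi-center, so local practice and each site's reading of the list could both affect who contributes 12-month data. Visits that were not held cannot be recovered at analysis.

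**Working it through.** **Step 1. The plan's own figure.** Section VII states "per study site an enrollment of 5 patients in one year can be expected" and assumes 8 sites: 5 × 8 = 40, which matches the stated total. This is a feasibility count. No healing, removal or dropout rate enters it.

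**Step 2. The texts side by side for removal after healing.**

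| Place | Covers removal after healing? | States whether follow-up continues? |
|---|---|---|
| Patient Withdrawal | Item is unqualified, so it can be read to include it | Gives a reason to withdraw; not worded as mandatory |
| Recommended Revision Procedure, footnote 1 | Expressly excluded from the procedure | No; only the procedure's own termination rule falls away |
| Explanted Device Return | Expressly excluded | No |

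A site can obey all three and either withdraw or keep the subject. The term reoperation is not defined, so the texts do not settle the question.

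**Step 3. Size of the loss of complication follow-up.** Inputs: N = 40 (Section VII), and r = number of healed subjects withdrawn for routine removal before month 12. The documents do not give r; 2 to 6 is assumed, with 4 as the middle value. Fraction lost = r/N:

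- r = 2: 2/40 = 5%
- r = 4: 4/40 = 10%
- r = 6: 6/40 = 15%

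These percentages restate the assumed r and are not an estimate.

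**Step 4. Shift in the 12-month healing rate.** Assume H = 34 of 40 healed (not in the documents), and that withdrawn subjects leave the denominator (the plan does not say). With everyone kept, the rate is H/N = 34/40 = 85.0%. With r withdrawn it is (H − r)/(N − r):

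| r | Rate | Shift (points) |
|---|---|---|
| 2 | 32/38 = 84.2% | −0.8 |
| 4 | 30/36 = 83.3% | −1.7 |
| 6 | 28/34 = 82.4% | −2.6 |

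Under these assumptions the shift is downward, so the healing rate would be understated.

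**Step 5. Sensitivity to the assumptions.** Assume 90% healed, with N = 40 or with N = 30 (the minimum in Section V, Study Population). Intervals are exact (Clopper-Pearson).

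| N | r | Rate | 95% interval |
|---|---|---|---|
| 40 | 0 | 36/40 = 90.0% | 76.3 to 97.2 |
| 40 | 4 | 32/36 = 88.9% | 73.9 to 96.9 |
| 40 | 8 | 28/32 = 87.5% | 71.0 to 96.5 |
| 30 | 0 | 27/30 = 90.0% | 73.5 to 97.9 |
| 30 | 4 | 23/26 = 88.5% | 69.8 to 97.6 |
| 30 | 8 | 19/22 = 86.4% | 65.1 to 97.1 |

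The shift is about 1 to 4 points. The interval at N = 40 with nobody withdrawn is already 97.2 − 76.3 = 20.9 points wide. The loss of evaluable subjects matters more than the change in the rate.

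**Step 6. The primary endpoint.** It is read at 3 months. It would be affected only if a subject healed and had the plate removed before that visit, which is much less plausible than later removal.

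**The case against.** The strongest defence is that nothing here conflicts. The withdrawal list gives reasons, not obligations. The footnote limits only the revision procedure and is silent on follow-up. Section VIII, Outcome of Events, pairs device removal with reoperation as the result of a medical event. That supports, without proving, a reading in which the withdrawal item covers event-driven removal only. On that reading elective removal lies outside the list. It can also be argued that ending follow-up once the screws are out is defensible in a study of the screws.

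Much of this stands. A reader might infer a direct contradiction, with one section forcing withdrawal and the other forcing retention. The documents do not support that, because neither section settles the subject's status. A reader might also infer that the best healers would leave. The documents show only that those leaving are healed, not that they heal better than other healed subjects. Nor do they say that any participating site removes plates routinely, or how often. Finally, the healing shift is small and rests on assumed inputs, and the analysis is descriptive with no control group.

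The defence does not remove the gap. A permissive list without a criterion leaves the choice to each site, and an undefined term allows either reading. Stopping follow-up at removal would also miss late events such as refracture, although complications are a secondary endpoint and confirming safety is part of the objective. If that is the intention, the protocol should say so.

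**Conclusion.** The point holds as an unreconciled ambiguity about study participation. Routine removal after healing is exempted from revision and from device return but not from the withdrawal list, and no text says whether the subject stays in follow-up. If such subjects are withdrawn, the missing 12-month data are informative by construction.

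On an assumed 2 to 6 affected of 40, 5 to 15% of the cohort would lack 12-month complication follow-up, all of them after a further operation. The healing rate would move by about 1 to 3 points if 34 of 40 were healed and withdrawn subjects left the denominator. The removal count, the healing rate and the denominator rule are all assumptions, so these figures show scale only. A reader might extend the concern to the primary result, but the 3-month endpoint precedes nearly all such removals. The correction is worth making because it is cheap and the data cannot be recovered later, not because the headline result is at risk.

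**What to change.** Reconcile the two sections on study participation:

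1. Add the exemption from footnote 1 to the device-removal item under Patient Withdrawal, so that removal after documented healing does not by itself end follow-up.
2. Record the date and reason of each removal on the case report form.
3. Keep the remaining scheduled visits and complication reporting for these subjects.
4. State in Section VII that 12-month status is reported as observed, with subjects seen after removal flagged. Healed status should not be carried forward: it is unnecessary if the visit takes place, and it could hide a refracture if it does not.

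The cost is one clause, one data item and one sentence in the statistical section. There is a small downside: callus images after removal are not comparable with earlier ones and need the same flag. The change concerns data collection only and proposes no rule on whether or when a device is removed.
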